#### Response:

Subjects enrolled in this study will receive intravenous fluid containing normal saline or lactated ringer's; both fluids are considered standard of care in the treatment of DKA. There is no other intervention for this study, we believe this study does not involve more than minimum risk to the participants. However, interim outcome analysis will be performed every 6 months to identify any problems that may associate with the study.

19.2 Describe what data are reviewed, including safety data, untoward events, and efficacy data.

In the interim analysis, patient outcomes will be reviewed as will any adverse events. An adverse event will be defined as any clinically important untoward medical occurrence in a child enrolled in this study different from what is expected in the clinical course of a child with DKA.

The investigator will evaluate any changes in laboratory values and physical signs and will determine if the change is clinically important and different from what is expected in the clinical course patients with DKA. Expected events for DKA are untoward clinical occurrences that are perceived by the investigator to occur with reasonable frequency in the day-to-day care of patients with DKA treated in an intensive care unit. Examples of expected events that may occur during treatment of DKA include cerebral edema, thrombotic events, acute kidney injury, hypokalemia, hypomagnesemia, hypophosphatemia, hypernatremia, hyponatremia, hyperchloremia, hyperglycemia and hypoglycemia.

Expected events will be evaluated monthly by the investigators and will not be considered reportable unless the event is considered by the investigator to be associated with the study procedures such as unexpectedly severe or more frequent than usually seen in the treatment of DKA. Organ failures related to DKA or an underlying condition will not be reported as adverse events. These will be captured in the data collection form but are routine occurrences during the treatment and recovery phase of DKA.

19.3 Describe the frequency of safety data collection.

Response:

As there is minimal risk related to this study, no regular safety data will be collected.

19.4 Describe who will review the safety data.

Response:

As there is minimal risk related to this study, no regular safety data will be collected nor will need review.

19.5 Describe the frequency or periodicity of review of cumulative safety data.

Response:

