The aggregate study data will be analyzed every 6 months. The frequency of all expected complications from DKA will be analyzed at that time.

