# 19.6 Describe the statistical tests for analyzing the safety data to determine whether harm is occurring.

#### Response:

Observed rates of expected events will be statistically compared using one-sided t-tests to previously reported rates of known complications associated with DKA to ensure that participants do not have a significantly higher rate of complications.

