# 19.7 Describe any conditions that trigger an immediate suspension of the research.

#### Response:

As the study protocol does not vary from the standard treatment, there is no obvious trigger or possible event that can be anticipated to lead to immediate suspension of the research.

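### Sections 19.3 and 19.4 rule out regular safety data collection and review, contradicting the monthly evaluation and six-monthly complication analysis set out elsewhere in section 19

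*Combined protocol and SAP*

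**What the plan says.** All of this is in section 19 of the combined protocol and SAP, apart from the data list in section 10.2.

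- **19.1:** "interim outcome analysis will be performed every 6 months to identify any problems". Section 19.2 adds that patient outcomes and adverse events are reviewed at that point.
- **19.2:** "Expected events will be evaluated monthly by the investigators". It gives eleven examples of expected events and says that organ failures, although not reported as adverse events, go on the data collection form.
- **19.3 (frequency of collection):** "As there is minimal risk related to this study, no regular safety data will be collected".
- **19.4 (who reviews):** "no regular safety data will be collected nor will need review".
- **19.5 (cumulative review):** aggregate study data are analysed every 6 months, and "The frequency of all expected complications from DKA will be analyzed at that time".
- **19.6 (tests for harm):** "Observed rates of expected events will be statistically compared using one-sided t-tests to previously reported rates". The stated purpose is to ensure that participants do not have a significantly higher complication rate.
- **10.2 (data collected):** all ED laboratories; PICU laboratory values including sodium, potassium, chloride, BUN, creatinine and glucose, with an open-ended et cetera; and, as outcomes, length of stay and resolution of acidosis.

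**The concern.** A frequency for all expected complications needs each event recorded as present or absent for every child. Sections 19.3 and 19.4 tell the study team that this is not done on any regular basis and that no review is needed. A team following those two answers, and using 10.2 as its list of items, would have no instruction to record cerebral edema or thrombosis systematically. The analysis in 19.5 and 19.6 would then run on whatever happened to be noted, and an undercount would look like a reassuringly low rate.

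Cerebral edema is the complication that section 3.1 links to 55-87% of DKA deaths. At stake is whether the trial can report a complete count of the complications it names, and whether anyone is responsible for looking at that count.

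**Working it through.** **1. The instructions side by side.** The plan states no safety sample size, power or alpha, so there is no figure to reproduce. The check is one of text.

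| Question | 19.3 / 19.4 | Elsewhere in section 19 |
|---|---|---|
| Are safety data collected regularly? | No | Needed for monthly evaluation (19.2) and six-monthly frequencies (19.5) |
| Does anyone review them? | Review not needed | Investigators monthly (19.2); six-monthly analysis, analyst not named (19.1, 19.5) |
| Are they tested? | Not addressed | Yes, against reported rates (19.6) |

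Monthly and six-monthly activities are regular, so the qualifier in 19.3 does not remove the conflict. Section 19.6 gives no timing; that its tests are run six-monthly is inferred from 19.5.

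**2. Which of the 11 listed events have a named data source in 10.2?**

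| Events in 19.2 | Named source in 10.2 | Count |
|---|---|---|
| Acute kidney injury | BUN, creatinine | 1 |
| Hypokalemia | Potassium | 1 |
| Hypernatremia, hyponatremia | Sodium | 2 |
| Hyperchloremia | Chloride | 1 |
| Hyperglycemia, hypoglycemia | Glucose | 2 |
| Hypomagnesemia, hypophosphatemia | In the PICU, at most the et cetera | 2 |
| Cerebral edema, thrombotic events | None named | 2 |

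7 + 2 + 2 = 11. The seven are covered within the laboratory collection window; for a child still in DKA after 32 hours, 10.2 ends PICU laboratory collection at about 36 hours from the first ED samples.

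**3. Scale.** Inputs: 104 children (5.1) and a cerebral edema rate of 0.3-1% (3.1), the only rate the protocol gives for an event on the 19.2 list.

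- Expected events: 104 × 0.003 = 0.31; 104 × 0.01 = 1.04.
- Chance of no event at all: 0.997^104 = 0.73; 0.99^104 = 0.35.

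**4. What the test could show with complete data.** Assumptions: exact binomial test, one-sided 0.05, arms pooled, and the 3.1 rate as reference. The critical count r is the smallest with P(X ≥ r | n, p0) ≤ 0.05.

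| Reference rate p0 | r at n = 104 | Actual alpha | Power at 2 × p0 | Power at 3 × p0 |
|---|---|---|---|---|
| 0.3% | 2 | 0.039 | 13% | 24% |
| 1% | 4 | 0.021 | 16% | 38% |

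Over 2 years with even accrual (assumed), the six-monthly cumulative looks would hold 104/4 = 26, then 52, 78 and 104 children. At 26, power against a doubled rate is 1% to 10%.

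**5. False signals.** If each of the 11 events is tested once at 0.05 and the tests are independent, the chance of at least one false signal is 1 − 0.95^11 = 0.43. Four such rounds give 1 − 0.95^44 = 0.90, an upper illustration because cumulative looks are correlated.

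**The case against.** The best defence is that 19.3 speaks only of regular safety data. All data come from the electronic record (10.4) and no extra laboratory tests are done, so 19.3 may mean only that there is no dedicated safety collection beyond the chart. That is a plausible intention and would fit the rest of the section. It is not what 19.4 says, however, since 19.4 also dismisses review. The defence supports rewording, not leaving the text alone. It may also be that the outcomes form listed in 10.3 already has complication fields; the form is not among the documents, so this cannot be excluded.

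A reader might go further and infer that there are no safety data, no reviewer and no consequence at all. The documents do not support that. Named laboratory values bear on seven of the eleven events, and organ failures go on the form. The investigators are the monthly reviewers. An event judged associated with study procedures, including one more frequent than usual, becomes reportable (19.2), and a child can be withdrawn to open-label fluids (20.1).

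A reader might also count 19.7 as part of the contradiction, because it says "there is no obvious trigger or possible event that can be anticipated to lead to immediate suspension of the research". It is not. Foreseeing no trigger for immediate suspension is compatible with monthly evaluation and six-monthly analysis.

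Finally, the plan promises no comparison of harms between arms: 19.6 compares with previously reported rates. Tabulation by arm is an addition, not the repair of a broken promise.

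**Conclusion.** The contradiction stands: 19.3 and 19.4 cannot be squared, as worded, with 19.1, 19.2, 19.5 and 19.6. Its practical effect is limited to two listed clinical events with no named data item (cerebral edema and thrombotic events), two laboratory events that are at best implied, and a six-monthly analysis with no named person to run it or act on it. This is worth correcting before the plan is relied on, but it is not a failure of the whole safety plan.

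With about 0.3 to 1.0 cerebral edema events expected, an incomplete count would be close to uninformative. It would be wrong to infer that one missed event could be the whole statistical signal: under the assumptions above, significance needs at least 2 or 4 events, and power against a doubled rate is only 13-16% even with full capture. The value of complete recording lies in an honest descriptive count, not in rescuing the 19.6 test. The size rests on the 0.3-1% rate in 3.1 applying to this PICU population, and on the unseen forms not already holding these fields.

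**What to change.** 1. Rewrite 19.3 and 19.4 to agree with 19.2, 19.5 and 19.6. State that every expected event listed in 19.2 is abstracted from the chart, for every child, as present or absent on the existing data form, if it is not already there. Add the same items to 10.2.
2. In 19.4, name the investigators as the monthly reviewers, and name the role that runs the six-monthly analysis.
3. Tabulate the counts by coded arm at each six-monthly review, as a low-cost addition.
4. State who is told of an apparent excess and who decides what follows. Do not link this automatically to the 19.6 t-test, which has no stated reference rates, safety alpha or multiplicity rule; section 17.1 gives only a general 0.05. With eleven events tested, a false signal would be common. Whether 19.7 should contain a suspension trigger, and which, is for the sponsor to set.

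The cost is a few sentences and slightly more chart abstraction from a record the study already uses. No new tests or committee are needed.

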# 19.6 Describe the statistical tests for analyzing the safety data to determine whether harm is occurring.

#### Response:

Observed rates of expected events will be statistically compared using one-sided t-tests to previously reported rates of known complications associated with DKA to ensure that participants do not have a significantly higher rate of complications.

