# 6.0 Inclusion and Exclusion Criteria

6.1 Describe the criteria that define who will be **included** in your final study sample.

NOTE: This may be done in bullet point fashion.

Response:

Inclusion criteria:

- 1. Age between 0 and 18 years
- 2. Diagnosis of DKA from Type I DM:
  - a. Venous pH less than 7.25
  - b. Ketonuria as confirmed on urine point-of-care testing or urinalysis
  - c. Hyperglycemia (Serum glucose > 200 mg/dl)
  - d. Serum bicarbonate <15 mmol/L
- 3. Need for PICU admission based on clinical discretion
- 6.2 Describe the criteria that define who will be **excluded** from your final study sample.

*NOTE: This may be done in bullet point fashion.* 

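### Section 19.6 tests yes/no complication rates with one-sided t-tests, which suit rare events poorly, and no saline-versus-Ringer's comparison of complications is written

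*Combined protocol and SAP*

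**What the plan says.** The statistical check on complications is in section 19.6: "Observed rates of expected events will be statistically compared using one-sided t-tests to previously reported rates of known complications associated with DKA". The section gives no alpha, no reference rates or source population, and no unit of counting (child, episode or measurement). Section 10.1 has electrolytes drawn every 2 hours, so the unit matters.

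The expected events are listed in 19.2. They run from cerebral edema, thrombotic events and acute kidney injury to "hypernatremia, hyponatremia, hyperchloremia, hyperglycemia and hypoglycemia". Hyperglycemia is also an entry criterion in section 6.1. Cerebral edema is the only listed event whose frequency the documents give: 0.3-1% of all DKA (section 3.1).

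On timing and review, the subsections disagree:
- 19.2: "Expected events will be evaluated monthly by the investigators".
- 19.5: "The aggregate study data will be analyzed every 6 months".
- 19.4: "no regular safety data will be collected nor will need review"; 19.3 likewise says that no regular safety data are collected.

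On consequences, 19.2 says that expected events "will not be considered reportable unless the event is considered by the investigator to be associated with the study procedures", and 19.7 says "there is no obvious trigger or possible event that can be anticipated to lead to immediate suspension of the research".

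Section 17.1 covers baseline comparisons, regression of the primary outcome and correlation of outcomes with chloride load. It names no safety event.

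**The concern.** A t-test on 0/1 data estimates its standard error from the observed proportion. When the reference rate is well under 1%, each extra case raises the standard error along with the difference, so the statistic climbs slowly and a real excess can pass as non-significant. With no cases the standard error is zero and there is no test at all.

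Section 19.6 is the only planned statistical check on how often complications occur, and its stated aim is to show that participants do not fare significantly worse than expected. For a rare, serious event, a non-significant result would say very little while appearing to say a good deal.

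The trial also randomizes children between two fluids, yet the written safety comparison pools both arms and sets them against outside rates. An excess confined to one arm is diluted, and no written analysis would show which fluid it belongs to.

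**Working it through.** The plan states no figure for this test, so there is none to reproduce. The check asks what the test would do as worded.

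**Inputs.** n = 104, 52 per arm (section 5.1). Illustrative references p0 = 0.3% and 1%, the two ends of the cerebral edema range in section 3.1; using them as p0 is an assumption. One-sided alpha 0.05 is also an assumption, carried over from 17.1. The test is read literally as one-sample with the sample SD.

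**Formulas.** For x cases, p = x/n:
- t-test: t = (p − p0) / sqrt(p(1 − p)/(n − 1)), with 103 df.
- Exact test: P(X ≥ x) for X ~ Binomial(n, p0).
- True size: P(X ≥ cut-off) at p0. Power: the same tail at the true rate.

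**Worked cases.**
- p0 = 0.3%, x = 3: p = 0.02885, SE = 0.01649, t = 1.567, t-test p = 0.060; exact p = 0.0039.
- p0 = 0.3%, x = 4: SE = 0.01895, t = 1.871, t-test p = 0.032, the first flag. The exact test already flags at x = 2 (p = 0.039).
- p0 = 1%, x = 4: t = 1.502, t-test p = 0.068; exact p = 0.021.
- p0 = 1%, x = 5: SE = 0.02108, t = 1.806, t-test p = 0.037, the first flag.

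| n = 104 | p0 = 0.3% (t / exact) | p0 = 1% (t / exact) |
|---|---|---|
| Cases needed to flag | 4 / 2 | 5 / 4 |
| True size | 0.0003 / 0.039 | 0.004 / 0.021 |
| Power, threefold excess in both arms | 1.5% / 24% | 20% / 38% |
| Power, twofold excess in both arms | 0.4% / 13% | 6% / 16% |

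**Zero cases.** (1 − p0)^104 = 0.997^104 = 0.73, and 0.99^104 = 0.35. These are the chances that the t-test cannot be computed when the true rate equals the reference.

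**Less rare events.** Cut-offs (t / exact) are 4/3 at 0.5%, 7/6 at 2%, 11/10 at 5% and 15/14 at 8%. In that range they differ by at most one case, and they coincide at some values (9/9 at 4%). They are identical at 10% (17), 20% (29), 30% (40), 40% (51) and 50% (61).

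**Dilution.** Suppose the rate is 3% in one arm (an assumption) and equals the reference in the other. The chance of a flag is then 0.093 (t) against 0.515 (exact) at 0.3%, and 0.058 against 0.155 at 1%.

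**By-arm comparison.** With 52 per arm, Fisher's two-sided p is 0.057 for 5 cases against 0 and 0.027 for 6 against 0.

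**The case against.** The strongest objection is that nothing turns on this p-value. Reportability under 19.2 is the investigator's judgement, on severity as well as frequency, and 19.7 names no trigger. A reader might infer that a severe case, or a cluster of cases, would go unreported because the t-test missed it. The documents do not support that, since a single severe event can be reported whatever 19.6 shows.

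A second objection is that the direction of the error depends on the literal reading. A z-test using the null variance would err the other way: at 1% it flags at 3 cases, with size 0.087. Nor is the 0.05 level stated in 19.6. At 0.01, the level used in the power statement, the t-test needs 6 to 8 cases over the 0.3-1% range against 3 to 5 for the exact test, so the conclusion does not depend on that choice.

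Third, the exact test is no cure. Its power for a threefold excess is only 24% at 0.3% and 38% at 1%.

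Finally, 17.1 correlates all outcomes with chloride load, and nothing bars a by-arm table. It would therefore be too strong to say that an excess could never be traced to a fluid. What stands is that 17.1 names no safety event and that no such comparison is written.

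These objections limit the weight of the point. They do not make the t-test suitable for rare events.

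**Conclusion.** The point holds in limited form and should be corrected. For an event as rare as 0.3%, the t-test needs twice as many cases as the exact test, and its true size is about 170 times below nominal (0.05/0.0003). At 1% the cut-offs differ by one case, and size is about 12 times below nominal (0.05/0.004). A reader might infer that the t-test is far too conservative for every listed event. It is not: the two tests agree at the values checked between 10% and 50%.

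The harm is false reassurance about rare complications, plus the absence of a written comparison between the randomized fluids. The contradiction between 19.3-19.4 and 19.2/19.5 is plain from the text and needs no calculation.

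The figures assume a one-sample t-test with the sample SD, one-sided 0.05, one look at n = 104 and one count per child. The 0.3-1% rate is for all DKA. The trial takes children needing PICU admission and excludes life-threatening cerebral edema at presentation, so that range illustrates the problem and is not a proposed benchmark.

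**What to change.** 1. In 19.6, replace the t-test with a one-sided exact binomial test, or an exact interval. Define each event and count each child once per event, with onset or worsening after randomization. Hyperglycemia then stays on the list, but hyperglycemia at entry does not count. Fix the alpha, reference rate, source and population in advance, choosing a population comparable with the trial's. State that a flag is a signal for review and not a formal test, because looks and events are multiple.
2. At the final analysis, report expected events by arm with counts and an exact interval for the risk difference, labelled descriptive. At 52 per arm, Fisher's test needs 6 against 0 to reach two-sided 0.05.
3. Reconcile 19.3-19.4 with 19.2 and 19.5, so that the protocol says once what is collected, who reviews it and when.

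**Cost.** This is mainly wording and event definitions. The data forms should be checked to confirm that they capture every listed event: 10.2 does not name cerebral edema, thrombosis, magnesium or phosphate, although 19.2 says that organ failures are recorded on the form. The exact test will also raise more false flags for rare events. With a 1% reference its size is 0.021 against 0.004 at one look. Over four assumed looks at 26, 52, 78 and 104 children, the chance of any false flag is 0.063 against 0.005. If the reference is set at 0.3% and the true rate is 1%, it flags 28% of the time against 2%, so the choice of reference population matters.

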# 3.0 Background

3.1 Provide the scientific or scholarly background, rationale, and significance of the research based on the existing literature and how it will contribute to existing knowledge. Describe any gaps in current knowledge. Include relevant preliminary findings or prior research by the investigator.

Response:

Diabetic Ketoacidosis occurs in approximately 30% of children with new onset type 1 diabetes mellitus (T1DM) and 5-10% of newly diagnosed children with type 2 diabetes [1]. DKA is a decompensated metabolic state resulting from insulin deficiency. DKA is characterized by acidosis, ketonemia, ketonuria, and hyperglycemia. Mortality from DKA in the United States is about 0.15%. Morbidity related to DKA is caused by shock, intestinal ischemia, cardiac arrhythmias, thrombosis, and cerebral edema [2, 3]. Clinically significant cerebral edema occurs in just 0.3-1% of all DKA, but results in 55-87% of all deaths related to DKA. The exact etiology of cerebral edema in DKA remains unclear, but it is consistently associated with osmotic shifts, hypoventilation, cerebral hypoperfusion, and administration of bicarbonate. With the intent to prevent shock, ischemia, and the thrombotic state, providers tend to administer large amounts of intravenous fluids in the form of 0.9% saline, also called normal saline, to patients in the initial treatment of DKA. Aggressive fluid administration has been shown to increase the risk of cerebral edema and does not reverse the primary metabolic deficiency driving the acidosis [4, 5].

During the treatment and recovery phases of DKA, the continued use of aggressive amounts of NS may be the mechanism by which patients develop a hyperchloremic metabolic acidosis (HMA) as NS contains a higher chloride concentration than serum. The detrimental clinical consequences of a high chloride load from intravenous fluids have been demonstrated in patients after trauma, in acute kidney injury, and in certain shock states [6, 7]. During HMA in

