#### Response:

All children with Diabetic ketoacidosis presenting to the John R. Oishei Children's Hospital (OCH) emergency department (ED) or transferred directly from outside facility to the pediatric intensive care unit (PICU) will screened for eligibility. Patients who are directly admitted to the PICU will represent 10% of the study sample with the remainder coming from the ED. As not all children in DKA are admitted to the PICU from the ED, it is estimated that approximately an additional 200 patients will be screened in the ER to achieve the target study size. In total, we anticipate screening approximately 310 patients with DKA for this study. 5.3 Justify the feasibility of recruiting the proposed number of eligible subjects within the anticipated recruitment period. For example, how many potential subjects do you have access to? What percentage of those potential subjects do you need to recruit?

Response:

Using historical patient volume data, it is estimated that approximately 2 years will be required to reach the target enrollment number.

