#### Response:

Exclusion criteria:

- 1. Physician discretion for any reason not listed here
- 2. Septic or hypovolemic shock
- 3. Signs of life-threatening cerebral edema or multi-organ failure upon presentation to the emergency room or pediatric intensive care unit
- 4. More than 2 hours since arrival to the PICU or from first provider contact in the emergency room
- 5. Pregnancy
- 6. Type II DM
- 7. Elevated anion gap metabolic acidosis from another source other than ketoacidosis
- 6.3 Indicate specifically whether you will include any of the following special populations in your study using the checkboxes below.

*NOTE: Members of special populations may not be targeted for enrollment in your study unless you indicate this in your inclusion criteria.* 

- Adults unable to consent
- Individuals who are not yet adults (infants, children, teenagers)
- Pregnant women
- □ Prisoners
- 6.4 Indicate whether you will include non-English speaking individuals in your study. **Provide justification if you will exclude non-English speaking individuals.**

In order to meet one of the primary ethical principles of equitable selection of subjects, non-English speaking individuals may **not** be routinely excluded from research as a matter of convenience.

In cases where the research is of therapeutic intent or is designed to investigate areas that would necessarily require certain populations who may not speak English, the researcher is required to make efforts to recruit and include non-English speaking individuals. However, there are studies in which it would be reasonable to limit subjects to those who speak English. Some examples include pilot studies, small unfunded studies with validated instruments not available in other languages, studies with numerous questionnaires, and some non-therapeutic studies which offer no direct benefit.

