#### Response:

Univariate analysis will be used to determine if the subjects in each treatment arm differ at baseline through t-test or Wilcoxon Rank Sum testing for continuous data and Chi-square testing for categorical data. Any differences will be controlled for in the analysis of the primary outcome (length of acidosis) using linear regression. All outcomes will be correlated with the overall chloride load given via intravenous fluids during DKA management. All analyses will be performed using IBM SPSS software, version 25 (Chicago, IL) and SAS (SAS Institute Inc., Cary, NC) with significance set at p<0.05.

17.2 If applicable, provide a power analysis.

*NOTE:* This may not apply to certain types of studies, including chart/records reviews, survey studies, or observational studies. This question is asked to elicit

whether the investigator has an adequate sample size to achieve the study objectives and justify a conclusion.

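### The harm test in section 19.6 uses reported complication rates for DKA with no limit on setting, severity or event timing, so its reference does not match the selected PICU children the trial enrols

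*Combined protocol and SAP*

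**What the plan says.** Section 19.6 gives the protocol's only statistical test for harm, a one-sided t-test in which the reference is "previously reported rates of known complications associated with DKA to ensure that participants do not have a significantly higher rate of complications". It names no source, rate, care setting, severity range or rule on when an event must start. Section 17.1 supplies the level, "with significance set at p<0.05", for all analyses. Section 19.5 applies the review to aggregate data every 6 months, and no between-arm safety comparison is planned.

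The only rate given for any listed expected event is in section 3.1: "Clinically significant cerebral edema occurs in just 0.3-1% of all DKA".

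The enrolled population is narrower. Section 6.1 requires venous pH below 7.25, serum bicarbonate below 15 mmol/L and "Need for PICU admission based on clinical discretion". Section 5.2 acknowledges that some children with DKA never reach the PICU. Section 6.2 excludes septic or hypovolemic shock and "Signs of life-threatening cerebral edema or multi-organ failure upon presentation to the emergency room or pediatric intensive care unit".

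Section 19.2 uses a similarly open reference. An expected event can become reportable if the investigator links it to study procedures, for example because it is "unexpectedly severe or more frequent than usually seen in the treatment of DKA".

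**The concern.** A test against an external rate is informative only if that rate is what the participants would have shown without the study intervention. Here two documented selections separate the participants from DKA in general, and they can act in opposite directions.

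- Selection for acidosis and PICU need may raise the baseline rate. Case mix alone could then be flagged as excess harm.
- Exclusions at presentation may lower the baseline for events tied to those features (edema, organ failure, shock). A real excess could then look normal against a published rate that includes children already affected on arrival.

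The choice of test does not cure this. An exact binomial test against the same reference carries the same mismatch. The result feeds the 6-monthly review and has the same basis as the reportability criterion in 19.2.

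**Working it through.** Section 19.6 states no figure, so there is none to reproduce. The check asks how the rule behaves when the reference is wrong.

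**Inputs from the protocol.** n = 104, 52 per arm (5.1); one-sided one-sample t-test (19.6); level 0.05 (17.1); cerebral edema 0.3-1% (3.1).

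**Assumptions not in the protocol.** A reference of 5% for a commoner expected event; a PICU baseline 2 or 3 times the reference; exclusions that halve the baseline.

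**Flagging threshold.** With x events, p = x/n and s = √[p(1−p)·n/(n−1)]. The test flags when (p − p0)/(s/√n) exceeds the t critical value on 103 df, 1.660.

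- p0 = 1%: x = 4 gives s = 0.193 and t = (0.0385 − 0.01)/(0.193/10.198) = 1.50, no flag. x = 5 gives s = 0.215 and t = 1.81, flag.
- p0 = 5%: x = 10 gives t = 1.59, no flag. x = 11 gives t = 1.84, flag.
- p0 = 0.3%: x = 3 gives t = 1.57, no flag. x = 4 gives t = 1.87, flag.

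**False flags with no added harm.** P(X ≥ threshold), X binomial(104, true baseline):

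| Reference | Flag at | Baseline = reference | Baseline ×2 | Baseline ×3 |
|---|---|---|---|---|
| 0.3% | 4 | 0.03% | 0.4% | 1.5% |
| 1% | 5 | 0.4% | 5.8% | 20% |
| 5% (assumed) | 11 | 1.5% | 47% | 93% |

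At an earlier look with n = 52, doubling the baseline takes the rate from 0.2% to 2.0% at a 1% reference, and from 1.5% to 26% at 5%.

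**Masking.** Suppose exclusions halve the baseline to p0/2 and the fluids double it, so the observed rate is p0. The harmed rate is held fixed and only the reference changes. With an exact binomial test at one-sided 0.05:

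- p0 = 1%: the unmatched reference needs 4 events, and P(X ≥ 4 | 1%) = 2.1%. The matched reference of 0.5% needs 3, and P(X ≥ 3 | 1%) = 8.7%.
- p0 = 0.3%: both references need 2 events, so both flag 3.9%. Matching gains nothing.
- p0 = 5% (assumed): 3.6% unmatched against 42% matched.

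The planned t-test does worse at 1%. It needs 5 events unmatched (0.4%). Matched to 0.5% it needs 4, where t = (0.0385 − 0.005)/(0.193/10.198) = 1.77, and it flags 2.1%.

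**Between-arm comparison.** With 52 per arm and one-sided 0.05, power for a doubling is about 11% (1% to 2%), 25% (5% to 10%), 41% (10% to 20%) and 72% (20% to 40%).

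**The case against.** The strongest reply is that 19.6 does not prescribe an all-DKA rate. The 0.3-1% figure is background, 19.6 does not cite it, and the sponsor could still choose PICU-based rates. Section 19.2 also describes expected events in terms of intensive care practice. It is right that nothing forces the wrong reference. But the intensive care wording settles which events count as expected, not the rate they are tested against. Nothing in section 19 requires a matched rate, and the one rate supplied is for all DKA.

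It is also fair that consequences are limited. Section 19.7 ties no suspension to a flag, and reportability under 19.2 rests on the investigator's judgement.

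A reader might infer three stronger things that the protocol does not support.

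- **That enrolment is the sickest third of DKA, with rates scaled by 310/110.** The screening estimate in section 5.2 reads "As not all children in DKA are admitted to the PICU from the ED, it is estimated that approximately an additional 200 patients will be" …, and comes to about 310 in all. It never states that 110 are PICU admissions. Were that so, enrolling 104 would need 104/110, about 95%, of them before refusals and exclusions. PICU need is a matter of discretion, and 6.2 removes some of the most severe presentations.
- **That cerebral edema will often trigger false alarms.** Large figures arise with an exact test that 19.6 does not specify. Under the planned t-test a 0.3% reference is almost never flagged.
- **That the bias has a known sign.** The two selections may partly cancel, and the protocol gives no data to say which prevails. Masking concerns events linked to the exclusions, not every listed electrolyte event. Section 6.2 also removes only life-threatening edema at presentation, so edema remains possible as a trial event.

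**Conclusion.** The concern holds in this form: the harm test is not restricted to a reference matching the enrolled children, so neither a flag nor a clean result can be attributed to the study fluids. The direction of the bias is unknown.

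Under the planned t-test at n = 104 and one-sided 0.05, a doubled baseline without added harm moves the false-flag rate from 0.4% to about 6% at a 1% reference, and from 1.5% to 47% at an assumed 5% reference. At 0.3% the effect is negligible. For missed harm at a 1% reference, an exact test flags 2.1% where a matched reference would give 8.7%; at 0.3% there is no difference. False alarms are thus mainly a matter for the commoner events. All these sizes depend on the assumed multipliers; the mismatch itself rests on the text of 3.1, 6.1, 6.2 and 19.6. The protocol should be amended, but the figures are illustrations, not predictions.

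**What to change.** 1. In 19.6, replace the reference with event rates in PICU-admitted children with DKA who meet 6.1 and none of the exclusions in 6.2, counting only events first identified after enrolment. Name the source for each event. Apply the same reference to the frequency criterion in 19.2.
2. Use the site's 55-patient PICU chart review (17.2) where it recorded the event. Section 17.2 reports only times to anion gap and acidosis resolution from it, so check first whether complications were captured.
3. Where only an all-DKA rate exists, report the comparison descriptively and not as evidence for or against harm. Do not write a 310/110 scaling into the protocol.
4. Add a comparison of event rates between the two randomised arms. Randomisation balances case mix and exclusions in expectation. It also addresses a weakness of pooling: if exclusions halve the baseline and one arm's rate doubles, the pooled rate is (0.5 + 1)/2 = 0.75 of the reference, and an exact test flags only 0.1-2.3% for references of 0.3% to 20%.

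The cost is rewording 19.2 and 19.6 and some tabulation. Sample size and treatment do not change, and no data are needed beyond the event frequencies 19.5 already calls for. The drawback is precision: a matched reference will be small, and the between-arm comparison has low power for rare events (about 11% for 1% to 2%). The plan should say so, so that a non-significant result is not read as evidence of safety.
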